9. Has adequate bone marrow reserve and organ function, based on local laboratory data, defined as within 14 days prior to Cycle 1 Day 1:

| Parameter | Laboratory Value |
|--|---|
| Platelet count | $\geq 100,000/\text{mm}^3$ or $\geq 100 \times 10^9/\text{L}$ (platelet transfusions are not allowed up to 14 days prior to Cycle 1 Day 1 to meet eligibility) |
| Hemoglobin | $\geq 9.0 \text{ g/dL}$ (transfusion and/or growth factor support is allowed) |
| Absolute neutrophil count | $\geq 1500/\text{mm}^3$ or $\geq 1.5 \times 10^9/\text{L}$ |
| SCr OR CrCl | SCr $\leq 1.5 \times \text{ULN}$, OR CrCl $\geq 30 \text{ mL/min}$ as calculated using the Cockcroft-Gault equation or measured CrCl; confirmation of CrCl is only required when creatinine is $>1.5 \times \text{ULN}$ |
| Alanine aminotransferase /aspartate aminotransferase | $\leq 3 \times \text{ULN}$ (if liver metastases are present, $\leq 5 \times \text{ULN}$) |
| Total bilirubin | $\leq 1.5 \times \text{ULN}$ if no liver metastases ($<3 \times \text{ULN}$ in the presence of documented Gilbert's syndrome [unconjugated hyperbilirubinemia] or liver metastases) |
| Serum albumin | $\geq 2.5 \text{ g/dL}$ |
| PT or PT-INR and aPTT/PTT | $\leq 1.5 \times \text{ULN}$ except for subjects on coumarin-derivative anticoagulants or other similar anticoagulant therapy, who must have PT-INR within therapeutic range as deemed appropriate by the Investigator |

aPTT = activated partial thromboplastin time; CrCl = creatinine clearance; INR = international normalized ratio; PT = prothrombin time; PTT = partial thromboplastin time; SCr = serum creatinine; ULN = upper limit of normal

10. If the subject is a female of childbearing potential, she must have a negative serum pregnancy test at screening and must be willing to use a highly effective form of birth control as detailed in Section 13.8, upon enrollment during the Treatment Period, and for 7 months following the last dose of study drug.

A female is considered of childbearing potential following menarche and until becoming postmenopausal (no menstrual period for a minimum of 12 months) unless permanently sterile (undergone a hysterectomy, bilateral salpingectomy or bilateral oophorectomy) with surgery at least 1 month before the first dose or confirmed by follicle-stimulating hormone (FSH) test. See Section [9.6](#) for further details regarding confirmation of post-menopausal status.

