| | Grade 3 and 4 | 
Permanently discontinue subject from study treatment.
 
Toxicity management:
 
 • Hospitalization required. • Promptly initiate empiric high-dose methylprednisolone IV treatment (eg, 500-1000 mg/day for 3 days), followed by at least 1.0 mg/kg/day of prednisone (or equivalent) for a minimum of 14 days or until complete resolution of clinical symptoms and chest CT findings, followed by gradual taper over at least 4 weeks. • Re-image as clinically indicated. • If still no improvement within 3 to 5 days, 
 • Re-consider additional work-up for alternative etiologies as described above. • Consider other immuno-suppressants and/or treat per local practice. |
| Eye disorders | | |
| Ocular | Grade 3 | 
Delay dose until resolved to \leqGrade 2, then:
 
 • If resolved in \leq7 days, resume U3-1402; • If resolved in $>$7 days, then reduce U3-1402 by 1 dose level. 
Ophthalmologist consultation as necessary.
 |
| | Grade 4 | 
Discontinue subject from U3-1402.
 
Ophthalmologist consultation as necessary.
 |
| Renal and urinary disorders | | |
| Creatinine increased | Grade 3 ($>3.0 \times$ baseline; $>3.0 - 6.0 \times$ ULN) | 
Delay dose until resolved to \leqGrade 1 or baseline, then reduce U3-1402 by 1 dose level.
 |
| | Grade 4 ($>6.0 \times$ ULN) | 
Discontinue subject from U3-1402.
 |
| Hepatobiliary disorders | | |
| AST or ALT increased without TBL increased | Grade 2 ($>3.0 - 5.0 \times$ ULN if baseline was normal; $>3.0 - 5.0 \times$ baseline if baseline was abnormal) | 
Continue U3-1402.
 
In subjects without liver metastasis, monitor AST/ALT 24 to 72 hours later, and continue regular monitoring until resolution.
 |

| | Worst Toxicity NCI-CTCAE Version 5.0 Grade (unless otherwise specified) | Schedule Modification for U3-1402 |
|----------------------|---|---|
| | Grade 3 ($>5.0 - 20.0 \times$ ULN if baseline was normal; $>5.0 - 20.0 \times$ baseline if baseline was abnormal) In subjects without liver metastases and subjects with liver metastases and baseline level $\leq 3 \times$ ULN. | Delay U3-1402 dose until resolved to \leq Grade 1, then: 
• If resolved in ≤ 7 days, resume U3-1402;• If resolved in >7 days, then reduce U3-1402 by 1 dose level. |

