| | $>8.0 - 20.0 \times$ ULN if baseline was normal; $>8.0 - 20.0 \times$ baseline if baseline was abnormal In subjects with liver metastases, if the baseline level was $> 3 \times$ ULN. | Delay U3-1402 dose until resolved to \leq baseline level, then: 
• If resolved in ≤ 7 days, resume U3-1402;• If resolved in >7 days, then reduce U3-1402 by 1 dose level. |
| | Grade 4 ($>20.0 \times$ ULN if baseline was normal; $>20.0 \times$ baseline if baseline was abnormal) | Discontinue subject from U3-1402. Gastroenterologist or hepatologist consultation as necessary. |
| TBL increased | Grade 2 ($>1.5 - 3.0 \times$ ULN if baseline was normal; $>1.5 - 3.0 \times$ baseline if baseline was abnormal) | If no documented Gilbert's syndrome or liver metastases at baseline, delay U3-1402 dose until resolved to \leq Grade 1, then: 
• If resolved in ≤ 7 days, resume U3-1402;• If resolved in >7 days, reduce U3-1402 by 1 dose level. If documented Gilbert's syndrome or liver metastases at baseline, continue U3-1402. |
| | Grade 3 ($>3.0 - 10.0 \times$ ULN if baseline was normal; $>3.0 - 10.0 \times$ baseline if baseline was abnormal) | If no documented Gilbert's syndrome or liver metastases at baseline, delay U3-1402 dose until resolved to \leq Grade 1, then: 
• If resolved in ≤ 7 days, reduce U3-1402 by 1 dose level;• If resolved in >7 days, discontinue subject from U3-1402. If documented Gilbert's syndrome or liver metastases at baseline, delay U3-1402 dose until resolved to \leq Grade 2, then: 
• If resolved in ≤ 7 days, reduce U3-1402 by 1 dose level;• If resolved in >7 days, discontinue subject from U3-1402. |

| | Worst Toxicity NCI-CTCAE Version 5.0 Grade (unless otherwise specified) | Schedule Modification for U3-1402 |
|--|--|--|
| | Grade 4 ($>10.0 \times \text{ULN}$ if baseline was normal; $>10.0 \times \text{baseline}$ if baseline was abnormal) | Discontinue subject from U3-1402. |

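### For subjects with liver metastases and baseline AST/ALT above 3 × ULN, Table 5.2 prints a branch that cannot occur and, separately, leaves >5.0 to 8.0 × baseline without an AST/ALT-specific row

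*Combined protocol and SAP*

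**What the plan says.** All of this sits in protocol Section 5.4.1.3, Table 5.2, in the rows for AST or ALT elevation without a bilirubin rise. Each row gives one range in multiples of ULN for a normal baseline and one in multiples of baseline for an abnormal baseline.

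- **Grade 2 row:** above 3.0 and up to 5.0 × baseline when baseline is abnormal; treatment continues. The range is not restricted by liver-metastasis status.
- **Grade 3 row:** above 5.0 and up to 20.0 × baseline when baseline is abnormal; the dose is delayed. The population is limited: "In subjects without liver metastases and subjects with liver metastases and baseline level" at or below 3 × ULN.
- **Subgroup row:** "In subjects with liver metastases, if the baseline level was" above 3 × ULN; the dose is delayed. Its first range is ">8.0 - 20.0 \times$ ULN if baseline was normal". Its second is above 8.0 and up to 20.0 × baseline when baseline is abnormal.
- **Grade 4 row:** above 20.0 × baseline when baseline is abnormal; treatment is discontinued.

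Section 4.1, criterion 9, allows a higher entry limit for AST/ALT "if liver metastases are present", namely 5 × ULN, measured within 14 days before Cycle 1 Day 1.

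**The concern.** The subgroup row is defined by a baseline above 3 × ULN, yet half of its trigger depends on a normal baseline. Separately, the neighbouring rows do not meet. One stops at 5.0 × baseline, the next excludes these subjects, and the row written for them begins only above 8.0 × baseline.

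Sections 1.2.2 and 9.3.2 name hepatotoxicity, or aminotransferase and bilirubin elevation, as an important potential risk. Table 5.2 is what a site consults to decide whether to continue or hold. If it has no AST/ALT row for a range of marked isolated elevation, sites must work out the rule themselves. Dose delays and reductions would then not rest on one stated rule across sites.

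**Working it through.** The plan gives no derived figure here, so there is nothing to reproduce. The check is to apply the rows literally.

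**Inputs.** Baseline B in the subgroup is above 3 × ULN (Table 5.2, subgroup row) and at most 5 × ULN (Section 4.1, criterion 9). The row limits are 3.0, 5.0, 8.0 and 20.0 × B (Table 5.2).

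**Step 1: which branch can operate.** The row requires B > 3 × ULN. A normal baseline does not exceed ULN. The two conditions cannot both hold, so only the range in multiples of baseline is live.

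**Step 2: convert to multiples of ULN.** Trigger in × ULN = row limit × B. Lower ends are exclusive and upper ends inclusive.

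| Baseline (× ULN) | Grade 2 row, continue (>3.0–5.0 × B) | No AST/ALT row (>5.0–8.0 × B) | Subgroup row, delay (>8.0–20.0 × B) | Grade 4 row, discontinue (>20.0 × B) |
|---|---|---|---|---|
| just above 3 | 9–15 | 15–24 | 24–60 | above 60 |
| 4 | 12–20 | 20–32 | 32–80 | above 80 |
| 5 | 15–25 | 25–40 | 40–100 | above 100 |

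The hold therefore starts above 8.0 × 3 = 24 × ULN at the low end and above 8.0 × 5 = 40 × ULN at the high end.

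**Step 3: test the gap.** Take B = 4 × ULN and an on-treatment value of 30 × ULN. The ratio is 30 / 4 = 7.5 × B. This is above the Grade 2 limit of 5.0 and below the subgroup start of 8.0, and the Grade 3 row does not apply because B > 3 × ULN. No AST/ALT-specific row matches.

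Now compare two subjects with liver metastases, both with a value of 16 × ULN. At B = 3.0 the ratio is 16 / 3.0 = 5.3 and the Grade 3 row says delay. At B = 3.01 the ratio is 16 / 3.01 = 5.3 and no AST/ALT row matches.

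**Step 4: are the two defects linked?** Delete the normal-baseline branch. The subgroup row still starts above 8.0 × B, the Grade 2 row still ends at 5.0 × B, and the Grade 3 row still excludes these subjects. Neither the 24–40 figure nor the gap changes, so the defects are independent.

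**Step 5: what if ULN multiples were meant for this subgroup?** Then 8 × ULN would equal 8 / 3 = 2.7 × B down to 8 / 5 = 1.6 × B, and the hold range would overlap the Grade 2 row. At B = 4 and a value of 16 × ULN (4 × B), one row would say delay and the other continue. Changing the reference in the subgroup row alone would therefore not make the table consistent.

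**The case against.** Several points on the other side have force.

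- **Causation.** A reader might infer that the impossible branch produces the high trigger and the gap. It does not (Step 4).
- **Divergent practice.** A reader might infer that sites will hold drug at values four-fold apart, since at B = 4 the ULN range starts above 8 × ULN and the baseline range above 32 × ULN. The documents do not support this prediction. Each branch is conditional on baseline status, so the text itself selects multiples of baseline, and nothing shows that sites would read it otherwise.
- **Under-protection.** A reader might infer that the rule protects least the subjects with the highest baselines. The AST/ALT and bilirubin rows all scale to an abnormal baseline, so absolute triggers rise with baseline throughout. The Grade 4 figures of 60–100 × ULN follow from the same convention. Whether any threshold is too high is a clinical judgement that the documents do not settle.
- **No instruction at all.** This goes too far. Table 5.2 also calls for a delay when AST/ALT is at least 3 × ULN with simultaneous total bilirubin above 2 × ULN. It does so again when AST/ALT exceeds 5 × ULN in subjects with liver metastases and known hepatitis B or C at baseline. The text after the table lets investigators consider reduction or discontinuation after discussion with the Medical Monitor.

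These provisions narrow the gap without closing it. The bilirubin and hepatitis rows act only under their own conditions, and the Medical Monitor provision is permissive.

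The Grade 3 row for other adverse events, laboratory findings included, is the best candidate for a fallback, but its reach is unclear because AST/ALT has its own rows. If it did cover Grade 3 AST/ALT from above 5.0 × baseline, the subgroup row's 8.0 start would have no function. The two rows also set different recovery targets: Grade 1 or baseline in one, baseline in the other.

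**Conclusion.** Table 5.2 is wrong as written for subjects with liver metastases and baseline AST/ALT above 3 × ULN, in two independent ways. One printed branch cannot occur, which leaves a hold starting at >24 to >40 × ULN. And isolated elevations above 5.0 and up to 8.0 × baseline fall in no AST/ALT-specific row: about 15–24 × ULN at a baseline just above 3 × ULN, 20–32 at 4 and 25–40 at 5.

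The upper figures assume that the baseline used for dosing stays within the 5 × ULN entry limit. Eligibility can rest on a value up to 14 days old. Table 5.2 does not define baseline; Section 11.5.2.2 defines it, for the laboratory analysis, as the last non-missing pre-treatment value. A later pre-dose value could therefore lie outside the limit.

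The affected group is narrow, since Section 5.4 applies these rules only to events judged related to study drug, and the documents give no frequency. The primary endpoint and its analysis are not touched. The point still warrants correction, because a stated safety rule skips a range of marked elevation in which other subjects would have the dose delayed at the same multiple of baseline.

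**What to change.** Reconcile the Grade 2, Grade 3 and subgroup AST/ALT rows of Table 5.2 with the subgroup definition and with the entry limit in Section 4.1, criterion 9:

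1. Remove or correct the normal-baseline branch in the subgroup row.
2. State once whether the multiple for this subgroup refers to ULN or to baseline, and check the result against the Grade 2 row, which would overlap under a ULN reference (Step 5).
3. Say which row governs values above 5.0 and up to 8.0 × baseline, and whether the row for other adverse events applies to AST/ALT.
4. Say which pre-treatment value counts as baseline for Table 5.2.

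The choice of threshold and action belongs to the sponsor's clinical team, and none is proposed here. The cost is a wording change to a few cells of one table in the next amendment, plus a notice to sites. The sample size and the planned analyses do not change.

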5.4. Dose Modifications (Dose Delay, Reduction, and/or Discontinuation)

All dose modifications (delay, reduction and/or discontinuation) should be based on the worst grade toxicity of the event preceding the dose modification. Dose modifications are applicable only to TEAEs that are assessed as related to use of U3-1402 by the Investigator(s). For non-drug related TEAEs, follow standard clinical practice. Appropriate clinical experts should be consulted as deemed necessary. All dose modifications must be recorded on the AE and drug administration electronic case report form (eCRF) pages.

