| AST or ALT increased and TBL increased | AST or ALT $\geq 3 \times \text{ULN}$ with simultaneous TBL $>2 \times \text{ULN}$ | 
Delay U3-1402 until drug-induced liver injury can be ruled out. The Investigator must consult with a gastroenterologist or hepatologist as needed, and the subject must be treated accordingly.
 
Monitor AST/ALT and TBL twice weekly until resolution or return to baseline.
 
It is strongly recommended to perform a full diagnostic workup, to exclude alternative causes such as viral or autoimmune hepatitis, alcoholic liver injury, biliary tract disorders, or hemodynamic abnormalities. Results from diagnostic workup (including, for example: INR, direct bilirubin, serologic tests for Hepatitis A, B, and C; alcohol use, ultrasound, MRI, CT scan, concomitant medication use, immunoglobulin levels, ECHO) must be recorded within the eCRF.
 
If drug-induced liver injury is ruled out, the subject must be treated accordingly, and resumption of U3-1402 may occur after discussion between the Investigator and Sponsor.
 
U3-1402 will be permanently discontinued if drug induced liver injury cannot be ruled out from diagnostic workup.
 |
| AST or ALT $> 3.0 \times \text{ULN}$ (if liver metastases are present, $>5 \times \text{ULN}$) for those subjects with known Hepatitis B and/or Hepatitis C infection at baseline | -- | 
Delay U3-1402 until reactivation of Hepatitis B and/or Hepatitis C can be ruled out.
 
Perform HBV DNA and/or HCV RNA to rule out reactivation of Hepatitis B and/or Hepatitis C, respectively.
 
Hepatologist and infectious disease consultations are recommended.
 
If reactivation of Hepatitis B and/or Hepatitis C is confirmed, permanently discontinue U3-1402.
 |
| Gastrointestinal disorders | | |
| Nausea | Grade 3 (inadequate oral caloric or fluid intake; tube feeding, TPN, or hospitalization indicated) | 
Delay U3-1402 until resolved to $\leq \text{Grade 1}$, and consider treatment with anti-emetics and/or corticosteroids as per Investigator's judgment and local/institutional guidelines, then:
 
 • If resolved to $\leq \text{Grade 1}$ in ≤ 14 days resume U3-1402; • If does not resolve to $\leq \text{Grade 1}$ in >14 days reduce U3-1402 dose by 1 level. |

| | Worst Toxicity NCI-CTCAE Version 5.0 Grade (unless otherwise specified) | Schedule Modification for U3-1402 |
|--|--|---|

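### Table 5.2 says both continue and delay for a related event with AST/ALT ≥3 × ULN and simultaneous Grade 2 bilirubin above 2 × ULN when the subject has liver metastases or Gilbert's syndrome at baseline

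*Combined protocol and SAP*

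**What the plan says.** All the dosing text is in Section 5.4 and Table 5.2 (Section 5.4.1.3).

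- **Scope.** Section 5.4 limits dose modifications to TEAEs that the Investigator judges related to U3-1402.
- **Bilirubin row, Grade 2.** The range is >1.5 to 3.0 × ULN if baseline was normal, or >1.5 to 3.0 × baseline if it was abnormal. For subjects with documented Gilbert's "syndrome or liver metastases at baseline, continue U3-1402". Other subjects have the dose delayed. AST and ALT are not mentioned.
- **Combined row.** The trigger is AST or ALT ≥3 × ULN with simultaneous bilirubin >2 × ULN. The action is "Delay U3-1402 until drug-induced liver injury can be ruled out", with "Monitor AST/ALT and TBL twice weekly until resolution or return to baseline". If drug-induced liver injury is excluded, treatment may resume after discussion with the Sponsor. If it cannot be excluded, U3-1402 is stopped for good. Neither liver metastases nor Gilbert's syndrome is exempted.
- **Aminotransferase rows.** These are titled "AST or ALT increased without TBL increased", which keeps them apart from the combined row. The bilirubin row has no matching limit.
- **Nearest rule of precedence.** Section 5.4 says that modifications "should be based on the worst grade toxicity of the event preceding the dose modification". Section 13.7 says to use the more severe CTCAE grade when two could apply.

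**The concern.** One bilirubin value can place the same related event in two rows with opposite dosing instructions. A site that follows the bilirubin row doses the subject. A site that follows the combined row holds the dose, starts the liver work-up and repeats AST/ALT and bilirubin twice weekly.

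This matters because Section 1.2.2 lists hepatotoxicity as an important potential risk, and Section 9.3.2 monitors these values as potential Hy's law. The Schedule of Events (Table 13.1, footnote l) requires chemistry results before each infusion, so the conflict arises exactly when the dosing decision is made. Section 13.2.9 bars deviations except to remove an immediate hazard, so a site needs one clear instruction. The subjects concerned are expected in the trial: Section 4.1, criterion 9, admits baseline bilirubin up to just below 3 × ULN in the presence of liver metastases or documented Gilbert's syndrome.

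The stake is the dosing decision and the monitoring interval. No endpoint, sample size or efficacy analysis is shown to depend on it.

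**Working it through.** The plan states no figure to reproduce. The check is whether the two trigger ranges intersect and, if they do, whether any text ranks the rows.

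**Step 1. Ranges, in multiples of ULN, with b = baseline bilirubin.**

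- Grade 2 bilirubin: >1.5 to 3.0 (normal baseline), or >1.5b to 3.0b (abnormal baseline).
- Combined row: bilirubin >2, given AST or ALT ≥3.
- Overlap: from max(2, 1.5) to 3.0 with a normal baseline; from max(2, 1.5b) to 3b with an abnormal one.

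**Step 2. Numbers, given AST or ALT ≥3 × ULN.**

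| Baseline bilirubin (× ULN) | Grade 2 band | Also meets the combined row | Share of band |
|---|---|---|---|
| Normal | >1.5 to 3.0 | >2.0 to 3.0 | 1.0/1.5 = 67% |
| 1.2 | >1.8 to 3.6 | >2.0 to 3.6 | 1.6/1.8 = 89% |
| 1.33 | >2.0 to 4.0 | >2.0 to 4.0 | 100% |
| 1.5 | >2.25 to 4.5 | >2.25 to 4.5 | 100% |
| 2.0 | >3.0 to 6.0 | >3.0 to 6.0 | 100% |
| 2.9 | >4.35 to 8.7 | >4.35 to 8.7 | 100% |

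The whole band overlaps once 1.5b ≥ 2, that is b ≥ 2/1.5 = 1.33. The shares describe the width of the band, not the proportion of subjects.

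**Step 3. One case taken through the text.** A subject has liver metastases and normal baselines. AST is 4 × ULN and bilirubin 2.5 × ULN on the same day, judged related.

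- AST falls in >3.0 to 5.0 × ULN, so it is Grade 2. Bilirubin falls in >1.5 to 3.0 × ULN, so it is Grade 2.
- The bilirubin row says continue.
- The combined row (4 ≥ 3 and 2.5 > 2) says delay.

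**Step 4. Does any text rank the rows?**

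- Section 5.4 (worst grade) and Section 13.7 (more severe grade) rank grades. Both analytes are Grade 2 here and the combined row carries no grade, so neither rule chooses.
- The text after Table 5.2 lets Investigators consider a reduction or discontinuation after discussion with the Medical Monitor. It does not require a hold.
- Section 9.3.2 requires reporting within 24 hours as an AESI and repeat laboratory confirmation. It sets no dosing action and no monitoring interval.

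The ranges intersect, and nothing states that the hold prevails.

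**The case against.** The strongest reply is that the combined row plainly governs. Table 5.2 is organised by toxicity, so an instruction to continue means only that this toxicity alone calls for no change. A subject with Grade 2 bilirubin and Grade 4 neutropenia also meets a continue row and a delay row, and nobody would read that as leave to dose. The combined row describes this exact laboratory state and grants no exemption, although rows above it do adjust for liver metastases.

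Much of this stands: the intent is probably clear, and most investigators would likely hold. It does not remove the conflict. In the neutropenia example two separate findings trigger the two rows; here a single bilirubin value helps to trigger both. Specificity also points both ways: the combined row is more specific on laboratory values, while the bilirubin row names this patient group. Because the aminotransferase rows carry an explicit limit and the bilirubin row does not, a reader could take the exception as deliberate.

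The reporting safeguards also count. Reporting within 24 hours alerts the Sponsor promptly and makes an unnoticed error less likely, but it does not mandate a hold.

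A reader might infer two wider problems, and the documents support neither.

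- **Conflicting doses at Grades 3 and 4.** A reader could set the bilirubin row's Grade 3 reduction against the combined row's resumption with no stated reduction. But that resumption is open only once drug-induced liver injury is excluded: "the subject must be treated accordingly, and resumption of U3-1402 may occur after discussion between the Investigator and Sponsor". Such an event would ordinarily no longer be related. Section 9.4.4 lets causality be updated, and Section 5.4 would then take the event out of Table 5.2. If liver injury cannot be excluded, the combined row ends in permanent discontinuation. At Grade 4, a hold pending work-up cancels nothing in the bilirubin row's discontinuation.
- **Subjects who enter with AST/ALT already ≥3 × ULN.** Entry allows up to 5 × ULN with liver metastases, so a bilirubin rise alone might seem to trigger both rows. This is arguable: a TEAE must start or worsen on treatment (Section 11.5.2.1), and the combined row's title speaks of an increase. The point does not rely on this case.

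**Conclusion.** The point holds for Grade 2 bilirubin only. For a related event in a subject with liver metastases or documented Gilbert's syndrome at baseline, AST or ALT ≥3 × ULN with simultaneous Grade 2 bilirubin above 2 × ULN meets one row that says continue and another that says delay. No text requires the hold to prevail.

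The conclusion rests on three conditions: the event is judged related, the elevations are simultaneous, and the two rows are read as written. The threshold arithmetic is firm. How often sites would follow the wrong row is not known, and the likely intent favours the hold. A reader might infer that the plan endorses dosing through potential Hy's law events; it does not, because the combined row orders a hold and the gap is only that its priority is unstated. The documents give neither the share of subjects with liver metastases nor an event rate, so no count of affected subjects can be given. This is a cheap safety clarification that should be made, not a flaw in the design.

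**What to change.** Preferred: add to the Grade 2 continue instruction in the bilirubin row: *unless AST or ALT is ≥3 × ULN with simultaneous TBL >2 × ULN, in which case hold U3-1402 and follow the combined row, including in subjects with liver metastases or Gilbert's syndrome.*

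Alternative: retitle the row *TBL increased without AST or ALT ≥3 × ULN and simultaneous TBL >2 × ULN*. A new title reaches beyond Grade 2, because Grades 3 and 4 always lie above 3.0 × ULN and so above 2 × ULN. If this route is taken, state that Grade 4 bilirubin discontinuation stays in force.

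Either change is one line in Table 5.2. Thresholds, visits, data collection and the restriction to related TEAEs stay as they are. The cost is some extra dose delays in subjects with liver metastases or Gilbert's syndrome, and permanent discontinuation under the combined row where drug-induced liver injury cannot be ruled out. With no event rate in the documents, that cost cannot be sized.
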